### **STUDY PROTOCOL**

The plant cell wall derived RG-I (from chicory or carrot) and maltodextrin (placebo) in capsuled form will be provided by the food company NutriLeads B.V (Wageningen, The Netherlands), which has run tests of safety of the products and warrants their food grade quality and safety. The administration of RG-I will be done via a human intervention study of parallel arms, randomized, placebo – controlled, double blinded design (proof of concept study).

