#### **Task 1: Evaluation of the prebiotic and intestinal inflammatory effects of RG-I daily supplementation**

The dietary fibre from different RG-I sources will be tested for its prebiotic and immunomodulatory potential. Thus, the effects of these fibres on short chain fatty acid (SCFA) profile, microbiota composition, microbiota-associated metabolites and intestinal inflammatory markers will be investigated.

In this Task, quantification of the aforementioned parameters will be performed in fecal samples which will be obtained from the study participants every week during their participation in the study. Furthermore, for this purpose subjects will complete questionnaires related to their diet; Food Frequency Questionnaire (an extract of the online tool that will be used for this purpose and a Gastrointestinal Symptom rating scale (GSRS) in the beginning and in the end of the interventional period.

**Task 2: Evaluation of the immunomodulatory, gut-brain interaction and lifestyle related effects of RG-I daily supplementation**

The dietary fibre from different RG-I sources will be tested for their immunomodulatory and lifestyle related effects. The effects of fibres on immune activation markers related peptides markers will be investigated from blood samples collected from the study participants. Furthermore, to assess the effects of RG-I supplementation in lifestyle, subjects will complete questionnaires related to their physical activity (IPAQ) and quality of life (EQ-5D-5L) at the beginning and at the end of the interventional period for this Task.

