**STATISTICAL ANALYSIS**

The groups will be of equal size and a time dependent analysis will be performed using a logistic generalized estimating equations (GEE) model via a stepwise approach. age, gender and BMI will be included AS confounding parameters. As fixed factors group (treatment versus placebo: dummy variable), time, time squared and the interaction between group and time will be taken into account. When the outcome does not warrant a GEE approach a Chi square analysis with expectation will be performed. Calculations will be done for a two-sided statistical evaluation at a significance level of 0.05.

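### For questionnaires taken only at start and end, the stated model compares change and leaves out the baseline score, which costs power that a score already collected would recover

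*Combined protocol and SAP*

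**What the plan says.** The Statistical Analysis section states that "a time dependent analysis will be performed using a logistic generalized estimating equations (GEE) model via a stepwise approach". The covariates are age, gender and BMI. The model terms begin "As fixed factors group (treatment versus placebo: dummy variable" and continue "time, time squared and the interaction between group and time will be taken into account". No coefficient or contrast is named as the treatment test, and the start value of the outcome is not listed for adjustment. There is also a fallback: "When the outcome does not warrant a GEE approach a Chi square analysis with expectation will be performed". The outcomes it covers are not named.

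The measurement schedules differ by outcome. Task 1 has the "Gastrointestinal Symptom rating scale (GSRS) in the beginning and in the end of the interventional period", with a diet questionnaire alongside. Task 2 says that "subjects will complete questionnaires related to their physical activity (IPAQ) and quality of life (EQ-5D-5L) at the beginning and at the end" of the intervention. Stool outcomes come from "fecal samples which will be obtained from the study participants every week during their participation in the study". The Study Protocol section describes a "human intervention study of parallel arms, randomized" and placebo-controlled.

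**The concern.** One list of terms is applied to outcomes with different schedules. With only two visits, the start score enters the GEE as an outcome and group has its own main effect. The term that carries the treatment effect is then the difference between arms in change from start to end. Age, gender and BMI do not stand in for the start score.

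Power is what is at stake. A comparison of change over-corrects for chance baseline differences whenever the start-to-end correlation is below 1, and so has a larger variance than an analysis with the start score as a covariate. That score is collected anyway.

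The weekly stool outcomes raise a smaller question. The arm difference is held to a straight line in time, and no single test is chosen from the group terms.

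**Working it through.** The documents give no sample size, power, effect size or correlation, so there is no planned figure to reproduce. Correlations, proportions, effect sizes and number of weeks below are assumptions. The two-sided 0.05 level and equal groups come from the Statistical Analysis section. Age, gender and BMI are left out of the calculations.

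**1. What the model estimates at two visits.** For visits at times a and b, t² = (a+b)t − ab, so time squared is an exact combination of intercept and time. The design [1, group, time, time², group×time] has rank 4 of 5. The redundancy puts no weight on group or group×time, so neither is affected. Group×time equals the difference in change: in one simulated data set the two were 0.1560 and 0.1560 (identity link), and 0.7307 and 0.7307 (logit link, change in log-odds).

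**2. Continuous score, equal variances at start and end.** In units of the score variance, with correlation ρ:

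- comparison of change: 2(1−ρ)
- baseline-adjusted: 1−ρ²
- ratio: 2(1−ρ)/(1−ρ²) = 2/(1+ρ)

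An adjusted analysis with 80% power has noncentrality (1.960+0.842)² ≈ 7.849. For the comparison of change this becomes 7.849(1+ρ)/2, and power is Φ(√noncentrality − 1.960).

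| ρ | Noncentrality | Power | Sample-size ratio |
|---|---|---|---|
| 0.3 | 5.102 | 62% | 1.54 |
| 0.5 | 5.887 | 68% | 1.33 |
| 0.7 | 6.672 | 73% | 1.18 |

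Testing group and group×time jointly has noncentrality 7.849 on 2 df, which gives 71% at any ρ.

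In 1,000 simulated null trials (ρ = 0.5, 50 per arm), the variance ratio was 1.35 against 1.33 in theory. The change estimate correlated −0.52 with chance baseline imbalance; the adjusted estimate correlated about 0.00.

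**3. Binary outcome under the logistic model.** These are large-sample calculations with control proportion 0.3 to 0.7 and log odds ratio 0.5 to 1.1, scaled to 80% power for logistic regression of the end value on group and start value.

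| Binary correlation | Power of group×time | Sample-size ratio |
|---|---|---|
| 0.3 | 60–68% | 1.34–1.59 |
| 0.5 | 67–73% | 1.19–1.36 |
| 0.7 | 74–78% | 1.05–1.16 |

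Simulation (10,000 runs per setting, log odds ratio 0.8, control proportion 0.3 and 0.5) gave 61–65% against 82% at correlation 0.3, and 70–72% against 82–83% at 0.5. Null rejection was 4.8–5.5%.

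**4. Weekly stool outcomes (secondary).** Assume a week-0 sample and an arm difference of 0 at week 0 and 1 from week 1 on. A straight line fitted to that difference under exchangeable correlation is the ordinary least-squares line. At 4 weeks the mean time is 2, the mean difference is 0.8 and the slope is 2.0/10 = 0.2, so the fitted last-week value is 0.8 + 2×0.2 = 1.20 where the truth is 1. The same calculation gives 1.20, 1.18 and 1.16 at 3, 6 and 8 weeks. This is for a continuous outcome.

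The choice of test also matters here. At 4 weeks and correlation 0.5, scaled to 80% for a baseline-adjusted final-week contrast, group×time alone has 58% power, the two group terms jointly 85%, and group alone 19%.

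**The case against.** The best defence is that a comparison of change is a legitimate analysis of a randomized trial. A reader might infer that leaving out the baseline score biases the result or inflates type I error. It does neither, and adjusting for baseline is a gain in efficiency only. At correlation 0.7 under the logistic model the gain is just 2 to 6 points (80% against 74–78%), and the conditional odds ratio then differs clearly from the marginal one. All of this stands and limits the size of the point.

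A reader might also infer that the rank deficiency undermines the treatment test for the questionnaires. It does not: software that drops the redundant column returns the same group and group-by-time results, and the stepwise wording may mean that the term is never forced in.

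Third, the plan does not say that the GEE applies to the questionnaires. They may fall under the chi-square fallback, and no cut-point is given for turning these scores into binary outcomes. That is true, and it makes the point conditional. It is not a rescue, because a chi-square test does not adjust for baseline either.

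Fourth, the unnamed test and undefined stepwise rule are, taken alone, mostly missing detail. The documents do not show that a test would be picked after seeing the data, nor that the weekly model is deficient. In the 4-week example its two group terms tested jointly have 85% power for a step effect and 81% for linear growth. The weekly point is therefore only that a test should be named, and that a last-week difference should not be read off the straight line.

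**Conclusion.** The concern holds as a matter of efficiency for GSRS, IPAQ and EQ-5D-5L, and for the diet questionnaire if it is analysed as an outcome. The stated model, if used for them, gives up power that the start score would recover: roughly 7 to 18 points for a continuous score (80% against 62–73%), and 2 to 20 points for a binary one (80% against 60–78%). That the start score is not a covariate follows from the text alone; the size of the loss rests on assumed correlations of 0.3 to 0.7, with equal variances in the continuous case. The calculations take two groups, as the single treatment-versus-placebo dummy implies. The Study Protocol section mentions chicory and carrot sources, so this should be confirmed. The redundancy of time squared is only a tidy-up. The 1.16 to 1.20 overstatement for weekly outcomes applies only if there is a week-0 sample, the effect plateaus early, and the last-week difference is taken from the straight-line fit. If the effect grows linearly, or sampling starts with the effect already at its plateau, the line fits exactly.

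**What to change.** **Start/end questionnaires.** Regress the end value on group, start value, age, gender and BMI: a linear model for a scored outcome, logistic for a binary one. Name the group coefficient as the treatment test, omit time squared, and state that the single dummy assumes two groups.

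**Weekly stool outcomes.** Name one treatment test in advance. If an arm difference at the last week is reported, estimate it from a model with time as categories, or from a baseline-adjusted contrast at that week.

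**Cost.** This changes the wording of the analysis plan and needs no new data. The regression uses only participants with both scores. The logistic group coefficient is a baseline-conditional odds ratio and must be labelled so. For a marginal odds ratio of 2.23 (log odds ratio 0.8) it is about 2.4, 2.9 or 4.4 at correlation 0.3, 0.5 or 0.7. If the marginal odds ratio is wanted, standardising the fitted model over the observed start values returns 2.23 with about the same power. For the weekly outcomes, the final-week contrast has somewhat less power than the two group terms tested jointly (80% against 85% for a step effect and 81% for linear growth, at 4 weeks and correlation 0.5), but it gives a single estimate that does not depend on a straight line.

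### The chi-square fallback states neither its unit of analysis nor its time point, and it leaves unused the starting status that the trial collects for most scheduled outcomes

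*Combined protocol and SAP*

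**What the plan says.** Under STATISTICAL ANALYSIS the main method is set out as follows: "a time dependent analysis will be performed using a logistic generalized estimating equations (GEE) model via a stepwise approach". Group, time, time squared and the group-by-time interaction are model terms, and "age, gender and BMI will be included AS confounding parameters". The fallback is one sentence: "When the outcome does not warrant a GEE approach a Chi square analysis with expectation will be performed". The error level is common to everything: "Calculations will be done for a two-sided statistical evaluation at a significance level of 0.05".

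The measurement schedules are in the two task descriptions:

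- **Task 1, fecal parameters** (SCFA, microbiota, metabolites, intestinal inflammatory markers): "fecal samples which will be obtained from the study participants every week during their participation in the study". The number of weeks is not given.
- **Task 1, diet and gut symptoms:** the food frequency questionnaire and the "Gastrointestinal Symptom rating scale (GSRS) in the beginning and in the end of the interventional period".
- **Task 2, IPAQ and EQ-5D-5L:** "at the beginning and at the end of the interventional period for this Task".
- **Task 2, immune markers:** these "will be investigated from blood samples collected from the study participants"; no timing is stated.

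The plan does not name the outcomes that go to the fallback, the rows or visit that enter the table, or the meaning of the words about expectation.

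**The concern.** A Pearson chi-square assumes that each count comes from a different, independent participant. It has no term for time, starting status or the covariates listed in the same paragraph. All outcomes with a stated schedule give at least two values per person. An analyst who applies the fallback to one of them must therefore decide how to reduce several rows to a table, and the plan gives no rule.

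Two things are at stake. If each participant contributes one row, the error rate is sound, but the plain test discards a starting value that the trial has already collected for the questionnaires and perhaps for the fecal outcomes. If several rows per participant enter the table, a nominal 0.05 no longer means a 5% false-positive risk. The sentence permits either, and both would be reported at the same significance level as the GEE results. The issue is separate from whether an outcome is continuous: it applies equally to a truly binary or categorical outcome.

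**Working it through.** **Inputs from the document.** Two-sided level 0.05; equal groups; parallel arms, so all of a person's rows fall in the same group; m = 2 rows per person for the questionnaires.

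**Assumed, because not stated.** Number of weekly samples (m = 4 as the main illustration, m = 8 as a longer series); within-person correlation rho of 0.3 to 0.7; participants per arm; response proportions.

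**Step 1. The plan's own figure.** The significance level is the only design number given: 2 × (1 − Φ(1.960)) = 0.050. There is no sample size or power to reproduce.

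**Step 2. Size if repeated rows were pooled.** Positive correlation inflates the variance of the between-arm difference by D = 1 + (m − 1) × rho. The true size is then 2 × (1 − Φ(1.960/√D)).

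| m | rho | D | 1.960/√D | size |
|---|---|---|---|---|
| 2 | 0.3 | 1.3 | 1.719 | 8.6% |
| 2 | 0.5 | 1.5 | 1.600 | 11.0% |
| 2 | 0.7 | 1.7 | 1.503 | 13.3% |
| 4 | 0.3 | 1.9 | 1.422 | 15.5% |
| 4 | 0.5 | 2.5 | 1.240 | 21.5% |
| 4 | 0.7 | 3.1 | 1.113 | 26.6% |

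The limits are wide. At rho 0.1 the size is 6.2% (m = 2) or 8.6% (m = 4). For m = 2 the ceiling, at rho = 1, is 16.6%. For m = 8 and rho 0.3 to 0.7 it is 26.6% to 42.0%.

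Beta-binomial simulation (40,000 trials per setting, 30 and 50 per arm, proportion 0.4) agrees: 11.1–11.2% for m = 2 and 21.7–22.0% for m = 4, both at rho 0.5. With a continuity correction these fall to 8.0–8.6% and 18.8–19.4%.

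**Step 3. Size with one row per person.** Here m = 1, so D = 1 and the size is 5% at any rho.

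**Step 4. What the starting status is worth.** The assumed case is a binary outcome with 40% positive at the beginning in both arms and 40% v 65% at the end. It was simulated with 20,000 replicates at 30, 40 and 60 per arm. The comparison is an end-only chi-square against a Mantel-Haenszel test stratified by starting status. Phi is the correlation between the beginning and end values.

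| phi | end-only power | stratified power | difference (points) |
|---|---|---|---|
| 0.54 | 50 / 64 / 80% | 61 / 74 / 90% | +11 / +10 / +10 |
| 0.33 | 50 / 64 / 81% | 53 / 66 / 83% | +3 / +2 / +2 |
| 0.19 | 51 / 64 / 80% | 50 / 63 / 80% | −1 / −1 / 0 |

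The size of the stratified test was about 5% throughout.

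**The case against.** The strongest reply is that the plan does not commit the error. It assigns repeated data to a GEE, and a binary outcome measured weekly is the textbook case for a logistic GEE. The fallback may therefore be meant for outcomes with one row per person, such as a derived responder status, a per-person summary or a blood marker taken once. A chi-square is valid there. This stands as far as intent goes. It does not settle the matter, because no such outcome is named and the sentence as written covers any outcome.

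Three stronger readings are tempting, and the documents do not support them:

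- **That the fallback doubles to quadruples the false-positive rate.** Pooling is nowhere stated, and the multiple depends on an assumed row count and correlation. For two-occasion questionnaires a fourfold rate is impossible: 16.6/5 = 3.3 at most.
- **That before-and-after tables within an arm will be tested as unpaired data.** Nothing in the plan describes such a comparison; its group term is treatment versus placebo.
- **That using one time point always loses power.** The third table row shows no loss at phi 0.19. Against a change score, the end value alone loses power only when the correlation exceeds 0.5.

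Two further points stand. A test stratified only on starting status still omits age, gender and BMI, and for weekly fecal outcomes it leaves the intermediate samples unused. Also, the words about expectation are undefined, so reading the test as a Pearson chi-square is reasonable but not certain.

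**Conclusion.** The concern holds as a gap in specification with a better method available at almost no cost; the plan contains no demonstrated inflation of error. For any outcome with a stated schedule, the fallback sentence must be completed before it can be applied, and it leaves open both a sound table and an unsound one. The pooled-row sizes in Step 2 are conditional on a practice that the plan does not describe and on assumed correlations of 0.3–0.7. The power gain rests on one assumed pair of end proportions and varies with the correlation, from about 10 points to none. The error rate of the stratified one-row test stays near 5% in every setting tried. The change should be made, although the issue concerns a secondary route of analysis in a proof-of-concept study.

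**What to change.** Replace the fallback sentence with wording of this kind: *An outcome not analysed by GEE is compared between arms with one row per participant, namely the status at the end of the intervention. The test is Cochran-Mantel-Haenszel, stratified by the participant's status at the beginning where that was measured, and an unstratified or exact test otherwise. Samples from different weeks are not pooled as independent rows.*

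The qualifier about the beginning is needed because blood timing is not stated, and the weekly fecal schedule does not say explicitly that a sample precedes the intervention.

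The cost is a few lines of analysis-plan wording, with no new data, visits or participants. There are two downsides. Strata without variation contribute no information, and power may fall by about a point where starting and end status are only weakly correlated.

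### The only stated fallback for graded GSRS and EQ-5D-5L answers is a chi-square, which on its ordinary reading ignores the order of the levels and drops the planned covariates

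*Combined protocol and SAP*

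**What the plan says.** The Statistical Analysis section sets out the main method as follows: "a time dependent analysis will be performed using a logistic generalized estimating equations (GEE) model via a stepwise approach". Age, gender and BMI enter as confounders. The fixed factors are group (treatment versus placebo), time, time squared and the group-by-time interaction. One alternative is named: "When the outcome does not warrant a GEE approach a Chi square analysis with expectation will be performed". No rank, trend, ordinal or linear method appears. Testing is two-sided at 0.05 and the groups are to be equal in size.

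Two graded questionnaires are among the measurements. Task 1 collects the "Gastrointestinal Symptom rating scale (GSRS) in the beginning and in the end of the interventional period". Task 2 collects "quality of life (EQ-5D-5L) at the beginning and at the end of the interventional period for this Task".

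The documents do not say which outcomes go to which method, how either questionnaire is scored (items, total or index), how many answer levels the GSRS has, or what sample size and power are planned.

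**The concern.** A standard logistic GEE models a two-category outcome. A graded answer enters it only after being cut in two, and no cut is defined. These questionnaires are also taken at only two time points, so time and time squared cannot both be estimated alongside an intercept. Both facts make it likely that they fall to the second method.

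The sentence on expectation most naturally means a Pearson test of observed against expected counts. Its statistic does not change if the answer levels are shuffled. With k levels and two groups it spends k − 1 degrees of freedom on a question that needs one: did the treated group shift up or down the scale? As written, it also leaves out age, gender and BMI, and makes no use of the baseline answer that the trial collects.

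At stake is a real, consistent shift in gut symptoms or quality of life being missed. That matters in a study described as proof of concept.

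**Working it through.** There is no stated power or sample size to reproduce, so this check is illustrative.

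**Inputs from the documents:** two-sided alpha of 0.05; equal groups; treatment versus placebo; chi-square as the only fallback.

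**Inputs assumed:** three to five answer levels (five for EQ-5D-5L is inferred only from its name); two arms; one end-of-intervention answer per participant; 80% power for the ordered test; an effect lying wholly along the ordering (a monotone shift).

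**Step 1. Noncentrality of the ordered test.** λ = (z for two-sided 0.05 + z for 80% power)² = (1.960 + 0.842)² ≈ 7.85.

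**Step 2. Same λ spread over k − 1 degrees of freedom.** Power = P(noncentral χ² with k − 1 df and noncentrality λ exceeds the 95th percentile of central χ² with k − 1 df).

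| Levels | df | Power at λ = 7.85 | Loss from 80% | λ needed for 80% | Sample-size ratio |
|---|---|---|---|---|---|
| 3 | 2 | 70.9% | 9.1 points | 9.63 | 9.63 / 7.85 = 1.23 |
| 4 | 3 | 64.5% | 15.5 points | 10.90 | 10.90 / 7.85 = 1.39 |
| 5 | 4 | 59.5% | 20.5 points | 11.94 | 11.94 / 7.85 = 1.52 |

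**Step 3. Sensitivity to reference power.** If the ordered test had 90% power (λ = 10.51), the losses would be 6.5, 11.6 and 16.0 points for three, four and five levels.

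**Step 4. Simulation check.** Answers were generated under a proportional-odds shift, with the odds ratio tuned so that a Wilcoxon rank-sum test had about 80% power. There were 20,000 replicates at each of 30, 50 and 100 per arm (all assumed). The loss from using the Pearson chi-square instead was:

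- three even levels: 9.1 to 9.7 points
- four even levels: 15.9 to 16.6 points
- five even levels: 20.9 to 22.5 points
- five skewed levels (70%, 20%, 7%, 2%, 1% in the reference arm): 20.9 to 23.9 points

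With no true effect, both tests rejected about 5% of the time for even levels. For the skewed answers the chi-square rejected only 2.9% to 3.8%, so part of its loss there comes from sparse cells.

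**Step 5. If the scale is cut in two first.** With five even levels, 50 per arm and an odds ratio of 2.75, power was 79.8% for Wilcoxon, 72.3% for a 2×2 chi-square (79.8 − 72.3 = 7.5 points lost) and 58.4% for the five-level chi-square.

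**Step 6. The opposite case.** One arm was spread evenly over five levels (20% each) and the other was concentrated in the middle (8%, 20%, 44%, 20%, 8%), with 50 per arm. The chi-square had 70.8% power and Wilcoxon 5.6%. The gain from an ordered test therefore depends on the effect being a shift in one direction.

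**The case against.** The strongest reply is that the plan never sends these questionnaires to the chi-square. The condition for using it is undefined, cumulative-logit versions of the GEE exist, and a scale could be dichotomised for either method. This stands as a limit: a reader might infer that an unordered test of GSRS and EQ-5D-5L is prescribed, and the documents do not say so. It does not rescue the text. An ordinal GEE is not named, a cut-point is not defined, and the time terms do not suit a two-visit measurement. Each way out needs an edit to the plan.

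A reader might also treat the power loss as a property of this trial. It is not, because the documents supply none of the quantities that determine it. The simulation also generated effects under proportional odds, which favours an ordered test, and it compared the chi-square with an unadjusted Wilcoxon test, not with the adjusted model recommended here.

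Nor is it right to say that a chi-square result carries no direction. The statistic is undirected, but the observed and expected counts show where the groups differ.

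Finally, the gap is wider than two questionnaires. Laboratory measurements such as short chain fatty acids and inflammatory markers suit neither named method without categorisation. That is true, but it does not weaken the point about ordered answers.

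**Conclusion.** The concern holds in a limited form. The only named alternative to a logistic GEE is a chi-square. Applied to ordered answers with more than two levels, it discards their order and, as written, the planned covariate adjustment. That these two questionnaires would go to it is an inference from having only two methods, not a stated assignment.

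For a monotone shift that an ordered test would detect with 80% power, the illustrative cost is about 9, 16 and 21 points of power with three, four and five levels. Put another way, the chi-square would need roughly 1.23 to 1.52 times the participants. The cost is smaller if the reference power is 90% or the scale is dichotomised, and it reverses for an effect that is not a one-directional shift. The direction of the loss under a monotone shift is well established by the calculation; its size in this trial is unknown.

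**What to change.** State the scoring of each questionnaire and replace the fallback sentence with text along these lines:

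> For ordered GSRS and EQ-5D-5L responses, treatment is compared with placebo using a proportional-odds model of the end-of-intervention level, adjusted for the baseline level, age, gender and BMI. Where a scale is analysed as a total or index score, a linear model of the end score is used, adjusted for the baseline score, age, gender and BMI. The chi-square test is used only for unordered categories.

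This takes a few sentences and no extra participants or measurements, since the baseline answers are already collected. The real cost is the trade-off in Step 6: an ordered test can have much less power than the chi-square for an effect that moves participants to both extremes at once. Tabulating the counts at each level by arm would let readers see such a pattern.

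### The plan names a stepwise logistic GEE for fecal outcomes that are quantified, and designates no outcome or model term as the primary test at its single 0.05 level

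*Combined protocol and SAP*

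**What the plan says.** The STATISTICAL ANALYSIS section describes one main method: "a time dependent analysis will be performed using a logistic generalized estimating equations (GEE) model via a stepwise approach". Age, gender and BMI enter as confounders. The model content is given as: "As fixed factors group (treatment versus placebo: dummy variable), time, time squared and the interaction between group and time will be taken into account". The only alternative is: "When the outcome does not warrant a GEE approach a Chi square analysis with expectation will be performed". The error-rate rule is a single sentence: "Calculations will be done for a two-sided statistical evaluation at a significance level of 0.05".

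The outcomes are in the two Task sections. Under Task 1, "the effects of these fibres on short chain fatty acid (SCFA) profile, microbiota composition, microbiota-associated metabolites and intestinal inflammatory markers will be investigated", and "quantification of the aforementioned parameters will be performed in fecal samples which will be obtained from the study participants every week". Task 1 adds the GSRS and a Food Frequency Questionnaire. Task 2 adds blood immune and peptide markers, the IPAQ and the EQ-5D-5L. The three scales (GSRS, IPAQ, EQ-5D-5L) are completed at the beginning and end of the intervention. No blood sampling schedule is given.

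The STUDY PROTOCOL section calls the trial proof of concept and gives two fiber sources, chicory or carrot. The available text names no primary outcome, no cut-point for a binary outcome, no criteria for the stepwise procedure and no multiplicity rule.

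**The concern.** There are two linked problems.

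The first is the match between model and data. A logistic model needs a binary outcome, and a chi-square test needs categories. Concentrations and abundances are neither until someone chooses a threshold. Dichotomising discards information, and a threshold chosen after the data are seen is one more route to a small p-value. Stepwise selection adds another: whether group-by-time stays in the model changes what the group coefficient means, because with the interaction present that coefficient is the group difference at the time origin.

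The second is that the 0.05 level is attached to no particular test. Without a designated outcome and contrast, a reader of the results could not tell a planned finding from a selected one, and an isolated p<0.05 would carry little weight.

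**Working it through.** **Model against outcomes.** Set side by side, Task 1 says the fecal parameters are quantified, while the analysis section offers a logistic GEE or a chi-square test. Both require categorical data, so the fallback does not rescue a quantitative outcome. No threshold is stated. The plan can be carried out for these outcomes only by adding a decision that it does not contain. This part is reasoning from the text, and no figure is attached to the information lost.

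**Counting outcome families.** There are four fecal families (SCFAs, microbiota, metabolites, gut inflammation markers), the GSRS, the blood markers, the IPAQ and the EQ-5D-5L: 4 + 1 + 1 + 2 = 8. The count is seven if the GSRS is not analysed as an outcome, nine if the Food Frequency Questionnaire is also an outcome, and ten if immune and peptide markers are counted apart as well.

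**Chance of at least one p<0.05.** The 0.05 level is a declared input, so there is no derived figure to reproduce. A single test returns 0.05. Assume all nulls are true, one test per family, and pooled RG-I versus placebo.

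- Independent tests: 1 − 0.95^k. For k = 8, 1 − 0.95^8 = 0.337. The expected number of false positives is 8 × 0.05 = 0.4.
- Equally correlated two-sided normal tests with assumed correlation ρ and c = 1.960: 1 − ∫ φ(u) [Φ((c − √ρ u)/√(1−ρ)) − Φ((−c − √ρ u)/√(1−ρ))]^k du.

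| Families | Independent | ρ = 0.3 | ρ = 0.5 | ρ = 0.8 |
|---|---|---|---|---|
| 7 | 30% | 27% | 23% | 15% |
| 8 | 34% | 30% | 25% | 16% |
| 9 | 37% | 33% | 27% | 17% |
| 10 | 40% | 35% | 29% | 17% |

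**Two candidate terms for one outcome.** If either the group or the group-by-time term may be read as the treatment test, one outcome alone carries 1 − 0.95² = 0.0975 if the two tests are independent, and 0.095, 0.091 or 0.078 at correlation 0.3, 0.5 or 0.8.

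Testing the components of a panel separately would raise the family figures. The documents give no component counts, so the increase cannot be stated. These percentages measure multiplicity only and say nothing about the size of the model problem.

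**The case against.** The strongest reply is that this is a proof-of-concept study that makes no confirmatory claim. Familywise control is not expected of such a study, and its absence is not in itself an error. That stands, and it sets the weight of the multiplicity part.

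Some pages were removed before review, so a primary outcome or a cut-point stated there cannot be excluded. That also stands and limits confidence. However, a primary outcome named elsewhere would not by itself settle the treatment term, the stepwise criteria or the choice of model.

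The word stepwise could mean a planned sequence of models and not data-driven selection. The text gives no criteria, so this reading is possible but unsupported.

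A reader might infer more than the documents allow:

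- *That no model term is named.* Four are listed. What is missing is a statement of which one is the treatment test.
- *That weekly sampling multiplies the tests.* The plan describes one longitudinal model with time terms and does not describe separate weekly tests. For the scales completed only at beginning and end, the time point is hardly in doubt.
- *That each source is tested separately against placebo, doubling the tests.* The number of arms is not stated, and the single treatment dummy implies pooling.

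**Conclusion.** The concern holds, with the model as its firmest part: as written, the analysis does not fit quantified fecal outcomes without an unstated dichotomisation, and its terms are left to an unspecified stepwise procedure. Replacing it would change the results.

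The missing primary test is a limit on interpretation. For eight families the chance of at least one nominal p<0.05 with no true effects is about 34% if independent and 16% to 30% at assumed correlations of 0.8 to 0.3. Across seven to ten families the range is about 15% to 40%. These figures rest on one test per family and on assumed correlations. Very small p-values, or concordant results across related outcomes, would still be informative.

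It would go too far to say that the plan contradicts itself or that the trial has no primary outcome. The proof-of-concept label rules out the first, and the removed pages leave the second unknown.

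**What to change.** Amend the plan before the data are analysed by group.

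1. **Model.** For quantitative outcomes, replace the logistic GEE and chi-square test with an identity-link GEE or linear mixed model, transforming where needed. Use a fixed, pre-specified set of terms including age, gender and BMI, and no stepwise selection. For the weekly fecal outcomes, adjust for the pre-intervention value if such a sample is collected; the text does not say that one is. For the GSRS, IPAQ and EQ-5D-5L, use ANCOVA of the end value on the beginning value. Do the same for blood markers if they have a beginning and an end sample.
2. **Primary test.** Designate one primary outcome and one treatment contrast, and reserve the 0.05 test for it. The model-based group difference at the final week and the group-by-time test are both valid contrasts; the sponsor chooses. State whether chicory and carrot are pooled, as the single dummy implies, or each tested against placebo with alpha split or in a fixed order.
3. **Everything else.** Apply Benjamini-Hochberg at 5% within each marker panel (SCFAs, taxa, metabolites, fecal inflammatory markers, blood markers). Label all non-primary results exploratory and report 95% CIs. The label is still needed: with five panels and all nulls true, the chance of at least one false discovery is 1 − 0.95^5 = 0.226 if the panels are independent. It is at most 5 × 0.05 = 0.25 in any case, provided the procedure holds 5% within each panel.

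**Cost.** Fewer secondary results will remain significant after adjustment. If alpha is split to 0.025 for each source, power per contrast falls at the same sample size. The documents state no power; from an assumed 80% it becomes Φ(0.842 + 1.960 − 2.241) = 0.71. A pooled contrast avoids that loss but supports no claim for a single source, although Task 1 and Task 2 set out to test different sources.
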